69. Beck, A. T., Steer, R. A., Ball, R. & Ranieri, W. F. Comparison of Beck Depression Inventories-IA and-II in Psychiatric Outpatients. *J. Pers. Assess.* **67**, 588–597 (1996).

71. Buysse, D. J., Reynolds, C. F., 3rd, Monk, T. H., Berman, S. R. & Kupfer, D. J. The Pittsburgh Sleep Quality Index: a new instrument for psychiatric practice and research. *Psychiatry Res.* **28**, 193–213 (1989).

72. Busby, D. M., Christensen, C., Crane, D. R. & Larson, J. H. A Revision of the Dyadic Adjustment Scale for Use with Distressed and Nondistressed Couples: Construct Hierarchy and Multidimensional Scales. *J. Marital Fam. Ther.* **21**, 289–308 (1995).

73. NEFF, K. D. The Development and Validation of a Scale to Measure Self-Compassion. *Self Identity* **2**, 223–250 (2003).

74. Sprecher, S. & Fehr, B. Compassionate love for close others and humanity. *J. Soc. Pers. Relatsh.* **22**, 629–651 (2005).

75. Ten Have, T. R. *et al.* Intent-to-Treat vs. Non-Intent-to-Treat Analyses under Treatment Non-Adherence in Mental Health Randomized Trials. *Psychiatr. Ann.* **38**, 772–783 (2008).

77. ATLAS.ti: The Qualitative Data Analysis Software. Available at: <http://www.atlasti.com/>. (Accessed: 7th April 2011)

78. Statistical Analysis Software, SAS/STAT | SAS. Available at: <http://www.sas.com/technologies/analytics/statistics/stat/index.html>. (Accessed: 7th April 2011)

Updated Statistical Analysis Plan

Under Aim 1, data for PRO (Patient Reported Outcomes) will be collected at Baseline, Weeks 1, 2, 3, 4, 5, 6, 7, 8, and 16. Pain, Stress, and Tension will be collected as a single-item scale measures, alongside intervention utilization, intervention satisfaction, and waitlist control pain/PTSD symptom mitigation activities weekly. All other PROs will be collected at Weeks 4 (Month 1), 8 (Month 2), and 16 (Month 4) (*see Table 1: Veteran and Partner Measures and Psychometric Properties in Protocol for further details*). General linear mixed models will be used with main effects terms for GROUP (MR vs. waitlist-control), TIME (continuous time measure from days from activation in protocol) and a GROUP x TIME interaction term (for rate of change).

Different correlation structures and functional forms of the effects of the MR program will be assessed using the information criteria and a final parsimonious model will be determined for final statistical inference. For H1.1, the primary outcome measure for pain will be the total score on the 19-item POQ, and its subscales. Additional analyses will be performed on the DVPRS, and the weekly 5-point Likert-scale Pain item. For H1.2, the primary outcome measure for PTSD will be total score on the 20-item PCL-5. For H1.2, the outcome measure for psychological symptoms is PSS; the outcome measure of sleep is PSQI; and the outcome measure for QOL is the SF12 and BDI. For H2.1, the outcome measure for relationship satisfaction is the RDAS. Additional analyses will be performed on the COS and CSS measures, the weekly 5-point Likert-scale Stress item, and the weekly 5-point Likert-scale Tension item.

Qualitative data analysis followed Inductive and deductive coding methods. A qualitative code book, consisting of known constructs from the literature and those that emerged inductively from the data, was created. Two trained qualitative researchers coded the data using the qualitative analysis software program, ATLAS.ti v. 22. To establish intercoder reliability at 80%, two qualitative researchers coded 20% of the interviews (initially every 5th transcript then randomly to ensure coding consistency) separately then compared codes to determine percent of agreement. Coded text in ATLAS.ti v. 22 was exported and further analyzed in Excel spreadsheets to develop themes. To enhance credibility, initial findings were presented during quarterly stakeholder meetings to provide input and facilitate refinement of findings.

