Screening interviews will assess the occurrence of chronic pain (pain for 6 months or more during the prior year) and symptoms of PTSD (diagnosed, treated or experienced symptoms of PTSD in the past 6-months); assess if they have visual, hearing, or other cognitive impairments; assess for previous diagnosis of moderate or severe TBI; recent history of psychosis; and determine availability of a partner and the dyad's interest in participation. Additional details on pain treatment history, severity and treatments of PTSD symptoms, potential TBI exposure, and recent use of complementary and alternative therapies for pain will be captured from the baseline data collection forms. In tandem, the fourth step (with waiver of consent) will allow chart review if needed for interested potential participants to: (1) confirm comorbid conditions (chronic pain and PTSD), (2)

determine substance use disorder treatment status, and (3) determine TBI diagnosis and severity to exclude individuals with moderate or severe TBI.

Eligible Veterans will be invited to participate after screening, be consented, and receive information to access the data collection site and determine their group assignment. This information will be provided at the completion of baseline data collection. Veterans and their partners will receive separate stipends for their time.

Sample: The sample will consist of 400 participants drawn from 200 dyads over approximately 4 months (MR Intervention Group) or approximately 4 months for (MR Control Group) at the Tampa VA. Women and minorities recruitment numbers will mirror site distribution based on sex and race, as this study is not powered to examine differences by race and sex. We anticipate considerable racial variability due to having three geographically diverse sites with markedly different census profiles. We anticipate a considerable representation of female participants with our invested partnership with women's physician [name], who has estimated the ability to recruit approximately 10% (n=25) of the overall sample at the Tampa site alone. This will make a considerable contribution to the knowledge of female Veterans which is often lacking in VA studies.

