Hypotheses Aims 1 & 2. All outcome measures (*primary and secondary*) under Aim 1 will be collected at baseline, 1, 2, and 4 months and are continuous variables. Therefore, general linear mixed models will be used with main effects terms for GROUP (MR vs. waitlist) and TIME (4-time points) and a GROUP x TIME interaction term (for rate of change). The models will also include site as a random effect. To assess whether the rate of change is curvilinear (i.e., the rate of change differs between time points), a quadratic parameter will be tested. Different correlation structures and functional forms of the effects of the MR program will be assessed using the information criteria and a final parsimonious model will be determined for final statistical inference. Initial effects of the MR program (baseline to 1-month) will be evaluated by analysis of covariance (ANCOVA). For H1.1, the primary outcome measure for pain will be total score on the 19-item POQ. For H1.2., the primary outcome measure for PTSD will be total score on the 20-item PCL-5. Subgroup analyses will be explored using similar methods and examination of severity of baseline pain and PTSD scores. These analyses will provide insight into subgroups in whom the MR program may be particularly beneficial. In a similar realm, analyses will be stratified by baseline median level of relationship satisfaction, as derived from total score on the 14-item RDAS. This will permit assessment of the effect of the MR intervention on potential improvement in relationship satisfaction among a cohort of dyads with presumably troubled relationships at entry. Moreover, using the weekly reports (8 weeks) of MR use and satisfaction with the MR program, the MR sample will be split above versus below the median for these two measures, and compared separately against the waitlist control condition at 2-months. This approach approximates a “per protocol” analysis in terms of recommended use of the MR program. In addition, especially for Aim 2 outcomes, we seek to examine whether dyads appear to show mutual benefits from the MR program. Therefore, multilevel models will be fit using an over-time dyadic model⁷⁸ in which individuals are nested within dyads and time is crossed with dyads (i.e., both Veteran and partner are assessed at the 4 time points). This analysis accounts for the non-independence due to the correlation between dyad members’ general levels on outcomes averaged over time, as well as the time-specific correlation between their outcomes (e.g., similarity caused by time-specific events).

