A) Human Subjects Involvement and Characteristics

In Aims 1-2 we estimate a recruitment sample size of 600 dyads, with approximately 33% over-sampling for attrition. We will recruit a sample of up to 200 Veteran/partner dyads (total 600 dyads) at each of the three sites to allow even numbers of dyads to be assigned to treatment and control arms. We will use a four-step process to purposively recruit study participants (see Figure 2). First, using a standard IRB approved procedure with a waiver of consent; a secondary administrative data query of the ICD9/10 conditions for chronic pain and PTSD will identify a sample pool of Veterans in the previous fiscal year. Cross-examination of the pain and PTSD cohorts for FY 2015 indicate a sample of 5,508 in Tampa who will be potential participants [Source: VSSC, Diagnosis Pyramid Analytics Report: Accessed 04/27/2017]. With our access levels and expertise, this process should take two weeks. Second, we will recruit from providers using signed letters from the PI. The provider will give the recruitment letter to the patient for him/her to follow up with the study team member to inquire about participating in the study. Study team members will mail the same recruitment letters to cohorts who have been identified in step one of the recruitment process to reduce burden of clinical partners and to reach those Veterans who don't often attend VA medical appointments. This helps provide an effective way to reach out to those Veterans with this type of diagnoses who are less likely or don't regularly receive care intervention. Potential participants who contact study staff after receiving a recruitment letter will be presented with information about the study to help them determine whether they'd like to participate in the study and provide a verbal consent and HIPPA authorization. Potential participants who have not responded to the letter may be contacted by their healthcare team for a follow-up. This procedure has been approved in other studies and provides an effective way to reach out to those Veterans with this type of diagnoses who are less likely or don't regularly receive care intervention. Based on our previous projects the process from initial sampling to recruitment and randomization should conservatively take three months.

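### The mixed model estimates a baseline GROUP difference that randomisation makes zero in expectation; at r = 0.5 a common baseline mean would cut the variance of GROUP x TIME by 17-22% if the effect is linear in time

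*Combined protocol and SAP*

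**What the plan says.** **Model.** The Updated Statistical Analysis Plan specifies "main effects terms for GROUP (MR vs. waitlist-control), TIME (continuous time measure from days from activation in protocol"), plus a GROUP x TIME interaction for rate of change. The protocol (Data Analysis, Hypotheses Aims 1 & 2) has the same structure: "general linear mixed models will be used with main effects terms for GROUP (MR vs. waitlist) and TIME (4-time points"). Those points are baseline and months 1, 2 and 4, so baseline is a response in the model.

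**Use of baseline elsewhere.** The same protocol paragraph says "Initial effects of the MR program (baseline to 1-month) will be evaluated by analysis of covariance (ANCOVA"). That covers the first month only, and the updated SAP does not repeat it. For Aim 2, "multilevel models will be fit using an over-time dyadic model", again with baseline among the four time points.

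**Form of the model.** It is left open: "Different correlation structures and functional forms of the effects of the MR program will be assessed using the information criteria". The protocol also tests a quadratic term.

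**Timing of allocation.** The Sampling section says of group assignment: "This information will be provided at the completion of baseline data collection".

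**Size.** "We will recruit a sample of up to 200 Veteran/partner dyads (total 600 dyads) at each of the three sites" (Human Subjects Involvement and Characteristics). The Sample Size Power Analysis assumes a within-subject correlation of 0.5 and about 33% attrition.

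**The concern.** With baseline as an outcome and GROUP as a free main effect, the linear model fits a separate starting level for each arm. Randomisation makes the true baseline means equal in expectation, so that parameter has a known value. Estimating it anyway adds variance to GROUP x TIME, the term that carries the treatment effect. The baseline data are collected in any case, and the plan already uses them as a covariate for the 1-month comparison, but not in the model meant for final inference. What is at stake is the width of the confidence interval on the primary pain outcome and the secondary outcomes.

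**Working it through.** **Inputs.** From the Sample Size Power Analysis: r = 0.5, 33% attrition, effect 0.38 SD, two-sided alpha 0.05. From the design: 600 dyads at 1:1, so 300 per arm. Visits at 0, 1, 2 and 4 months are scaled to t = 0, 0.25, 0.5, 1, so the slope difference is the month-4 difference in SD units. Assumed: unit variance, compound symmetry, and two dropout patterns. *Steady* means 11% stop after each of baseline, month 1 and month 2. *Early* means 33% give baseline only.

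**The plan's own figure.** With 600 x 0.67 / 2 = 201 per arm, the two-means formula gives a detectable effect of 2.80 x sqrt(2/201) = 0.28, and power of 96.8% at 0.38. The stated 80% power for 0.38 therefore does not follow from 600 dyads less 33%. It does match the planned slope contrast with 100 per arm: 2.80 x sqrt(2 x 0.914/100) = 0.379. That mismatch is a separate matter, because the variance ratio below does not depend on sample size.

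**Formula.** Let the information per participant for (intercept, slope) be X'V⁻¹X = [[a, b], [b, c]]. With n per arm, the variance of the slope difference is:
- free GROUP: (2/n) x a/(ac − b²)
- common baseline mean: (2/n) x 1/c
- proportional saving: b²/(ac)

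**Complete data, r = 0.5.** V⁻¹ = 2(I − 0.2J), the sum of t is 1.75 and the sum of t² is 1.3125.
- a = 2(4 − 0.2 x 16) = 1.6
- b = 2(1.75 − 0.2 x 4 x 1.75) = 0.7
- c = 2(1.3125 − 0.2 x 1.75²) = 1.4
- Free: 1.6/(2.24 − 0.49) = 0.914. Common: 1/1.4 = 0.714. Saving: 0.49/2.24 = 21.9%.

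**Early dropout, r = 0.5.** a = 0.67 x 1.6 + 0.33 = 1.402; b = 0.67 x 0.7 = 0.469; c = 0.67 x 1.4 = 0.938. The variance goes from 1.280 to 1.066, a saving of 16.7%. Steady dropout: 1.253 to 1.015, a saving of 19.0%.

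| r | complete | steady | early |
|---|---|---|---|
| 0.3 | 34% | 30% | 28% |
| 0.5 | 22% | 19% | 17% |
| 0.7 | 12% | 10% | 9% |

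**Weekly items** (baseline, weeks 1-8 and 16; r = 0.5). Complete: 0.675 to 0.598, about 11%. Early dropout: 0.981 to 0.892, about 9%.

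**Random slope** (four visits; intercept and residual variance 0.5 each; slope variance assumed at 0.01 to 0.10 per month squared). At zero intercept-slope correlation the saving is 8-19% with complete data and 6-17% with dropout. With complete data, correlation −0.5 gives 34% and 36% at the two ends of that range (37% at 0.03). Correlation +0.5 brings it down to about 0% at 0.10.

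**Size at 600 dyads, r = 0.5, 33% dropout.** Half-width = 1.96 x sqrt(2v/300).
- Steady: v = 1.253 gives 0.179; v = 1.015 gives 0.161.
- Early: v = 1.280 gives 0.181; v = 1.066 gives 0.165.
- Power for a 0.38 SD month-4 difference, Phi(0.38/SE − 1.96): 98.6% to 99.6% (steady) and 98.4% to 99.5% (early).

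**If the effect is not linear.** Take a flat effect of 0.38 at months 1, 2 and 4, with complete data.
- Free GROUP: (0.665 − 1.75 x 1.14/4)/(1.3125 − 1.75²/4) = 0.166/0.547 = 0.304 at every r. The GROUP term absorbs a further 0.152.
- Common baseline at r = 0.5: 2(0.665 − 0.2 x 1.75 x 1.14)/1.4 = 0.380. At r = 0.3 it is 0.422 and at r = 0.7 it is 0.345.
- With steady dropout the common-baseline values are 0.449, 0.408 and 0.373 at r = 0.3, 0.5 and 0.7, against 0.339, 0.337 and 0.335 with free GROUP.

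**The case against.** The strongest reply is that GROUP, TIME and GROUP x TIME is a standard rate-of-change model, that both texts name rate of change as the target, and that a tighter model is a preference. It stands that nothing in the plan is wrong here. It does not remove the gain in precision, which comes from data already collected.

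A second reply is that the comparison is fair only for a linear effect. This stands. For a curved or flat effect the two slopes estimate different quantities, and the common-baseline slope moves with the correlation, whereas the planned slope does not with complete data under compound symmetry. Because functional form is still to be chosen by information criteria, the percentages describe one candidate model.

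A third reply concerns partners. The Sampling sentence on disclosure is about eligible Veterans, and what it refers to also includes access to the survey site. The Human Subjects section repeats the step without the after-baseline condition. Nothing shows that partners finish baseline before the Veteran knows the arm. This also stands, and it limits how far the constraint can be applied.

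A reader might infer that the free GROUP term biases the result, inflates type I error, or leaves the trial short of power. The documents do not support this. GROUP x TIME already removes chance baseline differences, and at the stated 600 dyads power is high under either model. A reader might also take 6-19% as a general random-slope range. It holds only at zero intercept-slope correlation, and the documents give neither that correlation nor a slope variance.

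**Conclusion.** The point holds as an optional efficiency gain. For a linear effect under compound symmetry at the plan's r = 0.5, the planned model's slope variance for the four-visit outcomes is reducible by 22% with complete data and 17-19% under the two assumed 33% dropout patterns. The gain is larger at lower correlation and smaller at higher correlation, roughly halved for the weekly items, and undetermined under a random slope. In practice it takes about 0.02 SD off the month-4 half-width at 600 dyads. Confidence is high in the compound-symmetry arithmetic. It is lower in how large the gain will be once the covariance structure is chosen, and the comparison does not carry over unchanged to a non-linear effect.

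**What to change.** Add a short paragraph to the SAP for Veteran outcomes measured at baseline. The Self-Assessment of Change is excluded because Table 1 gives it no baseline.

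- **Continuous TIME:** set the baseline survey at time 0 and say how activation relates to it. Drop the GROUP main effect and keep GROUP x TIME. State that if the effect is not linear, this slope differs from the planned one and depends on the correlation and the dropout pattern.
- **Categorical TIME, if preferred:** allow no GROUP difference at baseline, keep GROUP x visit at months 1, 2 and 4, and name the deciding contrast. This avoids the dependence on correlation but replaces the rate-of-change target, so the choice must be explicit.
- **Partner outcomes and the over-time dyadic model:** use a separate common baseline mean for partners, and only where the partner's baseline was completed before the arm was disclosed.
- **Missing-data analyses:** carry the same constraint into the listwise and multiple-imputation analyses.

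The cost is that paragraph and a small change in model code, with no new data. Timing matters. The updated SAP already reports some work in the past tense ("Qualitative data analysis followed Inductive and deductive coding methods"), although this does not show that quantitative outcomes had been seen by arm. Date the change before they are examined by arm. If they already have been, keep the planned model as primary and report the constrained model as a sensitivity analysis.

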Sample Size Power Analysis: Aim 1&2, H1.1-H1.2 & H2.1 estimates of statistical power are based on Aim 1 and initially the primary outcome of pain. Whereas dyad is the unit of randomization, we assess power based on separate analyses for Veterans and partners (one approach used). There are 4 major intervals of assessment (baseline, 1, 2, and 4-months). At the beginning of this study, we estimated attrition based off of a previous MR trial that had less than 5% attrition. Based on early recruitment at the primary site, we have adjusted recruitment goals to allow for approximately 33% attrition, and uneven recruitment across the three study sites. Assuming within-subject (outcome measurement) correlation of 0.5, the proposed sample size will provide 80% power (2-sided type I error rate of 0.05) to detect a “small-to-medium” effect size of 0.38 (Cohen’s d). For analyses stratified by site (in addition to evaluation by random effect assessment), the study will provide 80% power to detect a “medium-to-large” effect size of 0.66. By way of comparison, the pilot data presented above describes large effect sizes ($d = 0.81$ for pain symptom reduction). While this effect size was based on a relatively small sample of comparable patients ($n < 15$) and within-subject assessment (paired t -test), it provides good assurance that the proposed sample size is sufficient to detect realistic, medium size effects should they exist with the MR program. For secondary outcomes, we will use a type I error rate of 0.01 for multiple comparisons. For the sample and our described assumptions, this will provide 80% power to detect a “medium” effect size of 0.45.⁵⁹

Sample Size: Qualitative- Aim 3 sample size relies on the quality and richness of information obtained.⁶⁰ Conceptual saturation is the goal of qualitative research, and depends on data to support interpretations. Saturation has been noted to occur within the first 12 interviews.^{60,61} Our team has extensive experience in evaluating electronic technologies, and have found recruiting high and low volume users provides the richest dataset. To ensure representative data, we will conduct telephone interviews with a purposive (e.g., high or low MR utilization group) sub-sample of up to 84 individuals to achieve representation at each site (approximately 28 individuals/site).

Data Collection Procedures. Data will be collected using (1) self-report surveys; and (2) telephone interviews.

(1) Self-reported Survey Data.

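### The form of the MR effect is chosen from the outcome data before the H1.1 test, so the test does not in general hold its two-sided 5% level

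*Combined protocol and SAP*

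**What the plan says.** Protocol, Data Analysis (Hypotheses Aims 1 & 2): a linear mixed model with GROUP, TIME and GROUP x TIME. To see whether change is curvilinear, "a quadratic parameter will be tested". Correlation structures and functional forms of the MR effect are then compared by information criteria, and "a final parsimonious model will be determined for final statistical inference".

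Updated Statistical Analysis Plan: the selection sentence is repeated, again that "functional forms of the effects of the MR program will be assessed using the information criteria and a final parsimonious model will be determined". The model terms are now "TIME (continuous time measure from days from activation in protocol) and a GROUP x TIME interaction term (for rate of change"). The quadratic is no longer mentioned.

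Protocol, Sample Size Power Analysis: the primary pain outcome is to have "80% power (2-sided type I error rate of 0.05) to detect a" small-to-medium effect of d = 0.38, assuming a within-subject correlation of 0.5.

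Neither document says which information criterion is meant, which forms are candidates, in what order selection runs, or which coefficient or joint test decides H1.1 afterwards. Neither adjusts for the selection step.

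**The concern.** Choosing a covariance structure by AIC or BIC is routine. Choosing the shape of the treatment effect that way is different, because the shape is judged on the same between-arm differences that H1.1 tests. If the arms diverge by chance in a curved pattern, the criterion tends to keep the curved form, and that pattern is then tested with the model it selected. A nominal 5% test after such a step is no longer a 5% test.

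The meaning of the result is also at stake. A linear slope and a two-degree-of-freedom curve test ask different questions. Until the data are in, a reader cannot tell which of them H1.1 will answer.

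**Working it through.** **Inputs from the documents.** Visits at 0, 1, 2 and 4 months; within-subject correlation r = 0.5; two-sided alpha 0.05; d = 0.38; 600 dyads; about 33% attrition; 1:1 allocation.

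**The plan's own figure.** 600 x 0.67 / 2 = 201 per arm. At r = 0.5 a change score has the variance of a single score, so power at d = 0.38 is Phi(0.38/sqrt(2/201) - 1.96) = 96.8%, not 80%. The stated 80% corresponds to about 109 per arm: Phi(0.38/sqrt(2/109) - 1.96) = 80.1%. That mismatch is a separate matter. Both sizes are used below as assumptions.

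**Type I error of select-then-test.** Assume complete data, known covariance and saturated visit means. Under the null, let Z_L be the standardised linear GROUP x TIME statistic and Z_Q that of the added quadratic GROUP x TIME term. They are independent N(0,1). The quadratic is kept if Z_Q^2 > k, with k = 2 for AIC and k = ln(N) for BIC. If it is dropped, reject when |Z_L| > 1.96. If it is kept, reject when Z_L^2 + Z_Q^2 > 5.991 (2 df).

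AIC, k = 2, which keeps the quadratic in 15.7% of null trials:
- quadratic dropped and rejected: 0.8427 x 0.05 = 0.0421
- quadratic kept with Z_Q^2 between 2 and 5.991, and rejected (numerical integration): 0.0186
- Z_Q^2 > 5.991, always rejected: 0.0144
- total: **0.075**, the same at any sample size.

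BIC, same steps:

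| Per arm | N | k = ln(N) | Type I error |
|---|---|---|---|
| 109 | 218 subjects | 5.38 | 6.7% |
| 109 | 872 observations | 6.77 | 5.9% |
| 201 | 402 subjects | 6.00 | 6.4% |
| 201 | 1608 observations | 7.38 | 5.6% |

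**Other readings of the same text.**
- Always linear, or always quadratic on 2 df: 5.0% each.
- AIC selection, then only the linear coefficient of the selected model is read: about 9%.
- Quadratic kept if its own p < 0.05, then the joint test: 7.2%.
- Quadratic in TIME common to both arms, with linear GROUP x TIME always the test: 5.0%.
- TIME main effect taking the same form as the interaction (simulated, r = 0.5): AIC 5.3-7.3%, BIC 5.0-6.0%. The low end arises with strong common curvature, because the quadratic is then selected most of the time whatever the arms do.

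**Power of fixed forms, assumed 109 per arm, d = 0.38.** Slope SE = sqrt((2/109) x 0.5/8.75) = 0.0324, where 8.75 is the sum of squares of the visit times about their mean. If the effect grows linearly to month 4, the slope is 0.38/4 = 0.095 per month, z = 2.93, power 83.5%. The fixed quadratic test on 2 df has noncentrality 2.93^2 = 8.6 and power 75%. If the full effect is present at months 1 and 2 and half is lost by month 4, the slope has 13% power and the quadratic 81%.

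**The case against.** The strongest reply is that the text can be read so that nothing is lost. The protocol speaks of one quadratic parameter, which may be a curve in TIME shared by both arms, with GROUP x TIME kept as the test of rate of change. That procedure holds 5.0%. The Updated SAP does not name the quadratic at all, and parsimony leans towards a BIC-like choice with the smaller excess. The calculations also assume complete data, known covariance and fixed visits, whereas the plan expects about 33% attrition and selects the correlation structure too.

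Much of this stands against attaching one number to the plan. It does not remove the point. The sentence in both documents applies selection to the form of the effects of the MR program, not only to the common time trend, and the SAP leaves the candidate set open.

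Three stronger readings should be resisted.
- A reader might infer that the trial's type I error is 7.5%, or higher with a longer candidate list. The documents give no list and no final contrast, so no single figure follows from them, and 7.5% is neither a floor nor a ceiling.
- A reader might set "TIME (4-time points) and a GROUP x TIME interaction term (for rate of change") in the protocol against continuous days in the SAP as a second open choice. The SAP section is headed as an update and is most naturally read as settling the coding.
- A reader might count the one-month ANCOVA as a rival primary test. The protocol presents it as addressing initial effects, and it plays no part in this error.

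**Conclusion.** The point holds. Followed as written, the plan lets the outcome data choose the form of the treatment effect and then tests H1.1 in the chosen model at an uncorrected 5%. That does not in general keep the stated level. With the one extra shape that the protocol names, placed in GROUP x TIME, the excess over 5% is about 2.5 points for AIC and 0.6 to 1.7 points for BIC under a joint test. It is about 4 points if the linear coefficient is read after AIC, and nil if the curve is common to both arms and the linear interaction is always tested. These sizes rest on r = 0.5, complete data, known covariance and, except for the common-curve case, saturated visit means. Confidence is high on the gap in wording and moderate on any particular percentage. The matter should be fixed, but it does not undermine the design.

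**What to change.** Amend the SAP before outcomes are examined by arm. The documents do not say whether that has happened; if it has, say so and report the test as specified after data access.

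1. Limit information criteria to the covariance structure and name the criterion.
2. Fix one H1.1 test on the POQ total at two-sided 5%. The natural default is the SAP's own linear GROUP x continuous TIME slope. The sponsor may instead name in advance a fixed quadratic GROUP x TIME test (2 df) or one contrast from a categorical-visit model.
3. Label every other shape fit as secondary or descriptive.

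The SAP wording "the primary outcome measure for pain will be the total score on the 19-item POQ, and its subscales" raises a separate multiplicity question and should be taken up on its own.

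No new data are needed. The cost is that no fixed test is best for every shape. At the assumed 109 per arm, the fixed quadratic gives up about 8 points to the slope under linear growth (75% versus 83.5%). The slope loses far more if the benefit comes early and fades (13% versus 81% in the example above). The sponsor should choose according to the time course it expects.
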